**Description of the Source Records that Will Be Used to Collect Data About Subjects**

Data will be collected from patient's medical records including history and physical examinations, laboratory and radiological information and psychiatric evaluations. We use EPIC as electronic medical record system. Patient information from the past will also be available on EPIC such as past medical records. A confidential data set will be maintained electronically to store patient information with separate study ID's for patients to maintain their confidentiality.

**Description of Data that Will Be Collected Including Long-Term Follow-Up**

These patients will be followed in the Seaver Autism Center four weeks post therapy and will continue to follow at this center if they are patients here. If not, they will return to their primary providers for standard care.

**Research Requires HIV Testing**      No

**13. Procedures - Genetic Testing**

Genetic Testing Will Be Performed No

***Guidance and Policies > Future Use Data Sharing and Genetic Research***

## **14. Procedures - Details**

**Surveys or Interviews** Yes

**Type of Instruments Being Used** Standardized

**Names of Standardized Instruments**

Vineland Adaptive Behavior Scale (VABS)

Description of Outcome Measures:

Parent-Rated Measures

The Aberrant Behavior Checklist

The Repetitive Behavior Scale-Revised (RBS-R)

The Sensory Profile

The Caregiver Top Three Concerns

Clinician-Rated Measures

The PMS Domain Specific Concerns

The Clinical Global Impression – Severity of Illness (CGI-S) and Clinical Global Impression – Improvement of Illness (CGI-I)

Peabody Picture Vocabulary Test (PPVT)

Objective Measures

Visual Evoked Potentials (VEPs)

Auditory Event Related Potentials (AERPs)

The Sensory Assessment for Neurodevelopmental Disorders (SAND)

Eye tracking

---

**Audio / Photo / Video Recording** No

---

**Deception** No

**Results of the Study Will Be Shared** No  
with Subjects or Others

**15. Procedures - Compensation**

Compensation for Participation      No

## **16. Consent - Obtaining Consent**

**Consent Process** Parental Permission / Child Assent

**Where and When Consent Will Be Obtained**

The investigator will describe the protocol to potential subjects' parents/guardians in person, although general information and assessment for eligibility can be carried out by phone if necessary. The Informed Consent may be read to the subjects' parent/guardians, but, in any event, the investigator or designee shall give the subjects' parents/guardians ample opportunity to inquire about details of the study and ask any questions before dating and signing the Informed Consent Form. The Informed Consent will be created with a level of language fully comprehensible to the prospective subjects' parents/guardians. Informed consent will be documented by the use of a written consent form approved by the IRB and signed and dated by the subjects' parents/guardians and by the person who conducted the informed consent discussion. The signature confirms the consent is based on information that has been understood. Each subject's signed informed consent form will be kept on file by the investigator for possible inspection by regulatory authorities. The parents/guardians will receive a copy of the signed and dated written informed consent form and any other written information provided to the subjects' parents/guardians, and will receive copies of any signed and dated consent form updates. Any amendments to the written information will be provided to subjects' parents/guardians.

**Waiting Period for Obtaining Consent**

Two weeks

**SOP HRP-090 Informed Consent Process for Research Is Being Used** Yes

**PPHS Worksheets, Checklists and SOPs**

**Process to Document Consent in Writing** Will Use Standard Template

**Non-English Speaking Participants Will Be Enrolled** No

**Justification for Not Enrolling Non-English Speaking Participants**

We will have our consenting forms only in English and do not want to enroll participants unable to understand English since it will not be fair for them to not have a complete understanding of the study. The various scales being used in the study are also available in English. Since this is only a pilot trial with 20 patients, we will enroll English speaking patients for this particular trial.

**17. Consent - Parental Permission**

**Permission To Be Obtained From** One Parent  
**Parental Permission Document** GH Consent version date 02-26-19.docx  
**Affirmation To Be Obtained From** None of the Children  
**Which of the Following Are True  
(Choose At Least One)** The capability of these children is so limited  
that they cannot reasonably be consulted.

**18. Consent - Documents****Consent Documents**

Type Consent form  
Name Consent for GH PMS trial  
Upload GH Consent version date 02-26-19.docx

**Consent Templates**

## **19. Data - Collection**

**Health Related Information Will Be Viewed, Recorded, or Generated** Yes

**Description of Health Information That Will Be Viewed, Recorded, or Generated**

We will view, record and generate information on patient's age, clinical status based on physical examination findings, laboratory parameters monitored during trial and radiological findings.

We will also generate and record information on psychological assessments of these patients and their VEP's results during the trial.

**Non-Health Related Information Will Be Viewed or Recorded** Yes

**Description of Non-Health Information That Will Be Viewed or Recorded**

Patient's name, demographic information including address, telephone number will be viewed and recorded.

**HIV / AIDS Related Information Will Be Viewed or Recorded** No

**Data That Will Be Viewed, Recorded, or Generated Contains ANY of the Following Directly Identifiable Information** Yes

**Will Be Viewed** Name, Medical Record Number, Address by street location, Telephone number, All Elements of Dates for Dates Directly Related to an Individual (i.e., Birth Date, Admission Date, Discharge Date), Email Address

**Will Be Recorded** Name, Medical Record Number, Address by street location, Telephone number, All Elements of Dates for Dates Directly Related to an Individual (i.e., Birth Date, Admission Date, Discharge Date), Email Address

**Data Collection Sheet** DATA COLLECTION SHEET edited.docx

***A Data Collection Sheet is required if you are either performing a retrospective review, or your study meets the category of exempt 4 research, or your study meets the category of expedited 5 research. Please upload it here.***

**Data Collection Source(s)** Participant, Medical Chart (Paper or Electronic), Clinical Database

## **20. Data - HIPAA**

**Obtaining HIPAA Authorization** Yes

**How PHI Will Be Protected from Improper Use or Disclosure**

Data will be stored in a secure data warehouse which will remain confidential. Only members of the study will have access to this information. Patients will be provided with a study ID which will maintain their confidentiality.

**PHI Will Be Destroyed at the Earliest Opportunity Consistent with the Research** No

**Justification for Retaining PHI Indefinitely**

This PHI may provide data to establish more long term studies in the field of growth hormone therapy in children with genetic forms of autism to look at its impact on their social withdrawal.

**PHI Will Be Shared** No

***PI must attest to the following.***

***\* I assure that the protected health information (PHI) will not be disclosed to any other person or entity not listed on this form except where required by law or for the authorized oversight of this research project. If at any time I want to reuse this PHI for other purposes or disclose it to other individuals or entities I will seek approval from the IRB.***

## **21. Data - Storage**

### **Location Where Data Will Be Stored**

Research data will be stored on a Microsoft Excel file on a secure server accessed via secure log-ins and passwords on hospital computers by the named personnel involved in the study. Only members of the research team will have access to the data. The subject will be identified by study number, and the link between the subject's full name and the study number will be stored in a locked room on the 4th floor of the Annenberg building.

**How will the data be stored?** With a Code That Can Be Linked to the Identity of the Participant

**Research Personnel Responsible for:** [name]

**Accessing Data** Yes

**Receipt or Transmission of Data** Yes

**Holding Code That Can Be Linked to Identity of Participants** Yes

**Research Personnel Responsible for:** [name]

**Accessing Data** Yes

**Receipt or Transmission of Data** Yes

**Holding Code That Can Be Linked to Identity of Participants** Yes

**Research Personnel Responsible for:** [name]

**Accessing Data** Yes

**Receipt or Transmission of Data** Yes

**Holding Code That Can Be Linked to Identity of Participants** Yes

### **Duration Data Will Be Stored**

10 years

### **Steps That Will Be Taken to Secure the Data During Storage, Use, and Transmission**

Data with PHI will only be stored on hospital computers. Data shared outside hospital networks will only have de-identified information. All data will only be accessible to study personnel.

### **Power Analysis/Data Analysis Plan (Including Any Statistical Procedures)**

The model for this design is baseline to week 12 change scores. To examine whether electrophysiological markers track changes in clinical profiles, we will fit an additional GLMM with VEP values included as a time-varying rather than baseline covariate. If treatment effects become less significant it will suggest that GH is acting on clinical outcomes through the biomarker. Finally, we will directly correlate week-12 change scores for VEP and clinical measures. All tests will use a two-sided # of .05.

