**Request Use of Clinical Research      No**  
**Unit Resources**

### **3. Summary - Background**

#### **Objectives**

1. To evaluate if growth hormone will adequately elevate IGF-1 levels within 12 weeks of therapy.  
Hypothesis: Growth hormone will cause a rise in IGF-1 levels within 12 weeks of therapy.

2. To evaluate efficacy of growth hormone induced elevation in IGF1 on social withdrawal as the primary outcome measure using the ABC – Social Withdrawal subscale (Aman et al., 1985).

Hypothesis: Growth hormone will produce the same effects in improvement in social withdrawal as compared to IGF-1.

3. To evaluate efficacy of Growth hormone induced elevation in IGF1 on repetitive behaviors using the Repetitive Behavior Scale-Revised (Bodfish), sensory reactivity using the Short Sensory Profile (Dunn) and the Sensory Assessment for Neurodevelopmental Disorders (Siper et al., 2017), and hyperactivity using the ABC-Hyperactivity subscale.

Hypothesis: Growth hormone will be associated with improvement across all outcomes comparable with the use of IGF-1.

4. To evaluate the effect of growth hormone therapy on visual evoked potentials and auditory event related potentials in children with Phelan McDermid Syndrome.

Hypothesis: Growth hormone will be associated with similar changes in visual evoked potentials and auditory event related potentials following 12 weeks trial as compared to IGF-1.

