#### **Primary and Secondary Study Endpoints**

1. Improvement in social withdrawal following growth hormone administration measured using the ABC - Social Withdrawal Subscale and repetitive behavior using the Repetitive Behavior Scale-Revised.
2. Improvement in other behavioral scales following growth hormone administration, such as the Short Sensory Profile, Sensory Assessment for Neurodevelopmental Disorders, and the ABC-Hyperactivity subscale as seen with the IGF-1 trial.
2. VEPs will show improvement in amplitudes in children with Phelan McDermid Syndrome following 12 weeks of growth hormone therapy, similar to the changes seen following IGF-1 therapy.

---

**Protocol Was Already Approved** No  

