## **12. Procedures - Narrative**

### **Description of the Study Design**

The proposed pilot will seek to recruit 20 children aged 2 to 12 years old with SHANK3 deletions or mutations and with radiographic evidence of open epiphyses. Phenotype definition will be conducted using a comprehensive assessment battery, including: (1) psychiatric evaluation; (2) clinical genetics evaluation; (3) neurological examination; (4) Vineland Adaptive Behavior Scales. The study will include newly recruited children in addition to those who have been previously recruited for the purposes of genetic studies by the Seaver Autism Center.

Patients recruited will have screening prior to trial and will then follow up at 4 weeks, 8 weeks and 12 weeks of therapy with growth hormone daily injections. A 4 week post therapy follow up will also be arranged.

Inclusion criteria:

Diagnosis: Pathogenic deletions or mutations of the SHANK3 gene confirmed by array CGH and/or direct sequencing.

Age Range: Cases will be between 2 and 12 years old at the time the phenotypic measures were collected.

Exclusion criteria:

Cases will be excluded if any of the following criteria are applicable:

closed epiphyses;

active or suspected neoplasia;

intracranial hypertension;

hepatic insufficiency;

renal insufficiency;

cardiomegaly/valvulopathy;

history of allergy to growth hormone or any component of the formulation (mecasermin);

history of extreme prematurity (<1000 grams) with associated early neo-natal complications, e.g. intra-cerebral hemorrhage, prolonged hypoxia, prolonged hypoglycemia;

patients with comorbid conditions who are deemed too medically compromised to tolerate the risk of experimental treatment with growth hormone.

Patient with visual problems that preclude the use of VEPs

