### **Drug Administration**

Growth hormone will be administered subcutaneously once daily using a 12-week single group design. No placebo will be used. The 12-week duration was selected because of our previous trial with IGF-1 showing effects in standardized behavior scales in that duration, hence establishing proof of concept.

The dose of daily growth hormone varies with the indication for therapy. Approved doses of growth hormone range from 0.16-0.25mg/kg/week for growth hormone deficient patients (Grimberg et al.; 2016) and up to 0.47 mg/kg/week for patients born small for gestational age.

In our proposed trial, we expect a majority of our patients to be growth hormone sufficient and therefore similar to the population of children with idiopathic short stature treated with growth hormone. We will recommend a dose of 0.15mg/kg/week divided daily for 2 weeks as a starting dose to ensure safety and tolerance. The dose will then be increased to 0.3mg/kg/week for 10 weeks, an average growth hormone dose in children with idiopathic short stature.

The growth hormone dose will be titrated based on IGF-1 levels monitored serially up to a maximum dose of 0.45mg/kg/week. (<http://www.ferringusa.com/wp-content/uploads/2018/07/ZOMACTON-PI-7-18.pdf> )

Drug dose is calculated on a mg/kg/week basis. Using Center for Disease Control average Weight-for-age statistics in typically developing children ages 2 to 12 years ([www.cdc.gov/growthcharts/cdc\\_charts.htm](http://www.cdc.gov/growthcharts/cdc_charts.htm)), the overall average weight across a representative sample of males and females in this age range is 24.65kg.

Average growth hormone dose for weeks 1-2: 0.15mg \* 24.65kg per week = 3.7 mg per week

Average growth hormone dose for weeks 3-10: 0.3mg \* 24.65kg per week = 7.4 mg per week

With a recruitment target of 20 patients, we anticipate the need for a total of 1628 mg of growth hormone with each person requiring about 81 mg of growth hormone in 12 weeks. We anticipate the need for 17 vials of growth hormone (10 mg per vial).

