### **Power Analysis**

Power is calculated for differences in baseline to week 12 change scores. Testing for treatment x time interactions and # at .05, we have 80% power to detect moderate to large effects.

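### A larger p value after adding VEP to the model does not show that growth hormone acts through VEP

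*Combined protocol and SAP*

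**What the plan says.** The Power Analysis/Data Analysis Plan in section 21 bases the analysis on change from baseline to week 12 and tests at two-sided 0.05. For the electrophysiology it says "we will fit an additional GLMM with VEP values included as a time-varying rather than baseline covariate", and it interprets the result as follows: "If treatment effects become less significant it will suggest that GH is acting on clinical outcomes through the biomarker". The next sentence adds a second analysis: "Finally, we will directly correlate week-12 change scores for VEP and clinical measures".

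Four other places bear on this:

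- **Design.** Drug Administration (section 12) describes treatment "using a 12-week single group design", without placebo.
- **Visits.** Description of the Study Design (section 12) says patients "will then follow up at 4 weeks, 8 weeks and 12 weeks of therapy". It does not say which visits supply VEP values to the model.
- **VEP endpoint.** Primary and Secondary Study Endpoints (section 3) predicts that "VEPs will show improvement in amplitudes in children with Phelan McDermid Syndrome following 12 weeks of growth hormone therapy". Objective 4 is likewise "To evaluate the effect of growth hormone therapy on visual evoked potentials" and on auditory potentials.
- **Power.** Power Analysis (section 21) says "we have 80% power to detect moderate to large effects", with no effect size or SD.

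The plan does not define how much weaker the effect must become. It specifies no indirect-effect estimate or confidence interval, and it does not make the inference depend on the correlation. The Attachments list names a separate Research Plan PDF, which was not available for this review.

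**The concern.** With no comparison arm, the treatment effect in this mixed model is the coefficient for time. If VEP amplitude moves over the same 12 weeks, VEP and time are partly collinear. Entering VEP then widens the standard error of the time coefficient, and the p value tends to rise whether or not the two changes are connected within children. The rule reads that rise as a sign of mediation.

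At stake is an exploratory claim about mechanism. The Objective Measures text in section 12 presents VEP as a measure of treatment response, so a reported pathway through VEP could influence later studies. As written, the plan allows that claim even if its own change-score correlation shows no association.

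**Working it through.** **Inputs from the documents.** n = 20, one arm, two-sided 0.05, 80% power, and visits at baseline and weeks 4, 8 and 12.

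**Assumptions.** The documents give no clinical effect size, SD, VEP shift, VEP visit schedule or VEP-clinical correlation. All SDs below are SDs of the baseline-to-week-12 change.

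**1. The plan's power figure.** With one arm, the matching test is a paired t test. For n = 20 its power is 0.799 at a mean change of 0.66 SD. The normal approximation gives (1.960 + 0.842)/√20 = 0.63 SD. This is compatible with the stated 80% for moderate to large effects, but with no effect size stated there is no exact figure to reproduce. I use 0.66 SD as the clinical change.

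**2. The mechanism, in change scores.** Regress clinical change D on VEP change X: D = a + bX. The effect after adjustment is the intercept, with

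SE(a)² = s² × (1/n + X̄²/Sxx).

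Take s = 1, Sxx = 19 and X̄ equal to the assumed VEP shift:

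- Shift 0: 1/20 = 0.0500, so t ≈ 0.66/√0.0500 = 2.95.
- Shift 0.66: 0.0500 + 0.4356/19 = 0.0729, so t ≈ 0.66/√0.0729 = 2.44.
- Shift 1: 0.0500 + 1/19 = 0.1026, so t ≈ 0.66/√0.1026 = 2.06.

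The critical value on 18 df is 2.10. A VEP with no link to outcome (b = 0) can therefore take a typical significant result to the border of non-significance.

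**3. Simulation with VEP unrelated to clinical change.** The mixed model was a random-intercept model fitted by REML with Wald z, 6,000 trials per setting. Ranges cover within-subject correlations of 0.4, 0.6 and 0.8 and, for 4 visits, linear or categorical time. The change-score regression used 100,000 trials. Loss of p<0.05 is a share of all trials.

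| VEP shift (SD) | Mixed model, 2 visits: p rises / p<0.05 lost | Mixed model, 4 visits: p rises / p<0.05 lost | Change-score regression: p rises / p<0.05 lost |
|---|---|---|---|
| 0 | 66-67% / 2% | 64-65% / 1% | 73.5% / 3.9% |
| 0.3 | 67-68% / 4-5% | 64-66% / 2-3% | 75.1% / 7.8% |
| 0.66 | 73-75% / 10-11% | 69-72% / 6% | 81.2% / 19.8% |
| 1.0 | 80-81% / 18-19% | 74-77% / 10-12% | 86.5% / 33.3% |

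Using a model without VEP or one with baseline VEP as the reference changes the mixed-model results by no more than 0.002. A repeat with separately written code (20,000 trials per setting, shifts 0, 0.5 and 1) also gave 64-81% and 1-19%. Among trials that were significant before VEP was added, the loss is 1-23%.

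**4. Chance benchmark.** With no clinical change at all, p rises in 49-56% of trials.

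**5. Does the rule separate a link from no link?** VEP shift 0.66 SD:

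| Criterion | No link | Correlation 0.5 | Correlation 0.3 |
|---|---|---|---|
| Any rise in p | 69-75% | 97-99% | – |
| p<0.05 lost, 2 visits | 10-11% | 30-36% | 21-25% |
| p<0.05 lost, 4 visits | 6% | 37-39% | 23-26% |
| Change-score correlation significant | about 5% | 64% | 25% |

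The correlation keeps its 5% error at every VEP shift tried (0.048-0.051).

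**The case against.** The strongest reply is about weight. The model is described as additional, the wording is hedged, and the setting is an open-label pilot in 20 children. The primary analysis, objective 4 and the VEP endpoint do not depend on the rule. All of that is right, and it limits the point to one exploratory inference.

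The reading of the rule can also be disputed. Counting any rise in p is the loosest interpretation, and roughly half of trials show one by chance. Even with no VEP shift p rises in 64-67%, so the expected shift explains only part of the excess. If the rule means losing p<0.05, it carries information: at a 0.66 SD shift it fires about three to six times as often with a correlation of 0.5 as with none. At shifts of 0 to 0.3 SD its false rate in the mixed model is 1-5%, no worse than the correlation test. The 19% needs a full 1 SD shift, two visits and no link. This stands, but the error still depends on how far VEP moves, which is not known in advance, and the plan does not say which reading applies.

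The figures rest on assumed inputs. If the shifts are expressed in visit-level SDs, with a within-subject correlation of 0.8, p rises in about 68-95% and significance is lost in 0-15%. The ranges move but the conclusion does not. The Research Plan PDF might define the rule more fully; nothing in the available text does.

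Finally, a significant correlation can occur when mean VEP does not change, so by itself it does not establish a pathway either. That is correct, and it is why the replacement should claim only an association.

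**Conclusion.** The rule is wrong as written. In a single-arm trial, a weaker time effect after adding VEP cannot distinguish a path through VEP from overlap between VEP and time. Read as any rise in p, it barely discriminates. Read as loss of p<0.05, it discriminates somewhat, with a false rate of 1-19% that depends on the VEP shift and the number of visits. At a 0.66 SD shift and correlation 0.5, the planned correlation has lower error and higher detection than either mixed-model version of the loss rule. At correlation 0.3 its detection is about the same as theirs, with lower error.

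The sizes depend on the assumed 0.66 SD clinical change, VEP shifts of 0 to 1 SD and 2 or 4 visits. The direction follows from the design. The consequence is confined to the exploratory biomarker inference.

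**What to change.** Delete the interpretive sentence and tie any statement about VEP to the correlation already planned. Suggested text:

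> *A link between VEP and clinical change is suggested only if the correlation of baseline-to-week-12 change scores is significant at two-sided 0.05, for one VEP measure and one clinical scale named in advance; the mean VEP change is reported alongside. With a single arm this is an exploratory association and cannot separate GH from time.*

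Naming one pair matters because the 5% error applies to a single test. The protocol describes three VEP peaks and its first endpoint names two scales, giving 3 × 2 = 6 pairs; if these were independent, the chance of at least one false positive would be 1 − 0.95⁶ ≈ 26%.

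If the time-varying mixed model is kept, report its estimates descriptively and draw no conclusion from the change in p. An indirect effect, or the change in the time coefficient, with a bootstrap confidence interval would be a reasonable exploratory alternative; its performance was not simulated here.

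An optional stricter version also requires a significant mean VEP change. Its error is at most about 5% (0.2-4.8% over the shifts tried).

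The cost is wording only, with no new data or visits. The drawback is that the biomarker claim becomes harder to make: detection is about 64% at correlation 0.5 and 25% at 0.3. With the optional condition and a 0.66 SD shift, it falls to about 50% and 20%.
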